8.5.2 Safety Analysis Populations

The All-Subjects-as-Treated (ASaT) population consists of all randomized subjects who received at least one dose of MK-8962 and will be used for the analysis of safety data in this study.

At least one laboratory or vital sign measurement obtained subsequent to at least one dose of study treatment is required for inclusion in the analysis of each specific parameter. To assess change from baseline, a baseline measurement is also required.

All-Subjects-Pharmacokinetically-Evaluable (ASPE) population: Consists of all subjects from the ASaT group, for whom at least one PK parameter can be calculated according to the protocol and who did not have any protocol violation interfering with PK. Subjects included in the ASaT group, but excluded from the ASPE group will be listed including the reason(s) for exclusion.

The final determination on major protocol deviations interfering with PK, and thereby the composition of the ASPE population, will be made prior to the finalization of the database and will be documented in a separate memo.

8.6 Statistical Methods

Statistical testing and inference for safety analyses are described in 8.6.2.

8.6.1 Statistical Methods for Efficacy Analyses

All efficacy analyses will be performed for the FAS.

This section describes the statistical methods that address the primary and secondary objectives. Methods related to exploratory objectives will be described in the supplemental SAP.

8.6.1.1 Primary Efficacy Analysis

The mean change from Day 1 (Baseline) in log-transformed testicular volume will be analyzed using a mixed model with a fixed effect for baseline and time point and a random effect for subject. For each time point (i.e., Week 1-64), the mean change from Day 1 to that time point and the associated 95% confidence interval (CI) will be calculated. The geometric mean increase in testicular volume and its 95% CI will be obtained by exponentiation.

The mean change from the first day of combined treatment (Week 12) to Week 64 in log-transformed testicular volume will also be analyzed using a mixed model with a fixed effect for time point and a random effect for subject. For each time point, the mean change from Week 12 to that time point and the associated 95% CI will be calculated. The geometric mean increase in testicular volume and its 95% CI will be obtained by exponentiation.

An unstructured covariance matrix will be used to model the correlation among repeated measurements. In the event of model convergence issues, other covariance structures will be considered.

In addition, the change from Day 1 to Week 12 (i.e., during the priming phase alone) in log-transformed testicular volume will be summarized. The associated geometric mean increase and its 95% CI will be obtained by exponentiation.

Sensitivity analyses

A supportive analysis using only subjects who completed Week 64 will be performed for the primary efficacy endpoint only if there are at least 5 such completers. The mean change from Day 1 (Baseline) to Week 64 in log-transformed testicular volume will be analyzed using an Analysis of Covariance (ANCOVA) model including baseline as a covariate. The geometric mean change in testicular volume and its 95% CI will be obtained by exponentiation. The mean change from the first day of combined treatment (Week 12) to Week 64 will also be analyzed for the completers only.

Changes in log-transformed testicular volume will also be analyzed separately for the left and right testes using the same mixed model as for the primary analysis. Last Observation Carried Forward (LOCF) approaches will be used to investigate the robustness of the results for the testicular volume (as the sum of volumes of left and right testes) as well as for the left and right testes separately.

Accounting for Missing Data

Assuming that data are Missing at Random (MAR), the mixed model for the primary efficacy analysis accounts for missing data.

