8.3 Hypotheses/Estimation

Objectives of the study are stated in Section 3.0. This is an estimation study, no hypothesis will be tested.

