Endpoint/Variable (Description, Time Point)	Primary vs. Supportive Approach [†]	Statistical Method	Analysis Population	Missing Data Approach
Primary Endpoint				
Change from Baseline to Week 64 in log-transformed testicular volume (measured as the sum of volumes of left and right testes by ultrasound);	P	Linear Mixed Model [#]	FAS	Model-based
Change from Baseline to Week 64 in log-transformed testicular volume (measured as the sum of volumes of left and right testes by ultrasound);	S	Linear Mixed Model [#]	FAS	LOCF ^{\$\$}
Change from Baseline to Week 64 in log-transformed testicular volume (measured as the sum of volumes of left and right testes by ultrasound);	S	ANCOVA	Completers	N/A

[†] P=Primary approach; S=Supportive approach.

[#] Linear Mixed Model with terms for treatment.

^{\$\$} LOCF = last-observation-carried-forward method.

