8.9 Sample Size and Power Calculations

8.9.1 Sample Size and Power for Efficacy Analyses

This is an estimation study.

Assuming a screen failure rate of 50-60%, approximately 30-40 subjects will be screened to enroll approximately 15. Assuming a discontinuation rate of 30%, it is estimated that 10 subjects will complete the study. If the discontinuation rate exceeds 30%, enrollment will be re-opened to assure the target number of completers (i.e., 10). The total number of enrolled subjects shall not exceed 35.

[Table 7](#) summarizes estimates of the geometric mean increase in testicular volume (mL) under various assumptions. These calculations are based on a difference in paired means with 10 completed subjects at an overall one-sided 2.5% alpha-level and are carried out using [SAS v9.3].

In P031 (adult men with HH) the estimated geometric mean increase in testicular volume from Day 1 to Week 52 was 2.30 (95% CI: 2.03-2.62). This corresponds to a difference from baseline and SD (both on log-scale) of 0.84 and 0.47, respectively. These finding are consistent with similar results observed in other studies [1, 17] where at least a doubling of mean testicular volume of adolescent males was observed after recFSH treatment. Based upon these experiences, a 2-fold (or greater) increase in testicular volume is expected. Applying generally similar SD as observed in P031, the study should be able to estimate a larger than 2-fold increase with the lower margin of the 95% CI excluding an increase of less than 1.7-fold. The CI, with 10 completers, suggests reasonable precision to estimate the change in testicular volume.

Table 7 The 95% Confidence Limits for Geometric Mean Increase in Testicular Volume (mL) by Underlying Difference and SD Assumptions (log-scale) for 10 Completers

Underlying Difference from Baseline to Week 64 (log-scale)	Underlying SD (log-scale)	Geometric Mean Increase	95% Confidence Limit†
0.4	0.45	1.49	1.18, 1.89
	0.5		1.15, 1.93
	0.55		1.12, 1.99
0.5	0.45	1.65	1.30, 2.08
	0.5		1.27, 2.14
	0.55		1.24, 2.19
0.6	0.45	1.82	1.44, 2.30
	0.5		1.40, 2.36
	0.55		1.37, 2.43
0.7	0.45	2.01	1.59, 2.54
	0.5		1.55, 2.61
	0.55		1.51, 2.68
0.8	0.45	2.23	1.76, 2.81
	0.5		1.72, 2.89
	0.55		1.67, 2.96

† One-sided 95% CI based on a difference in paired means.

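### The baseline covariate in the single-arm primary model may make the nominal 95% CI for the geometric mean increase too narrow, by an amount the documents do not fix

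*Combined protocol and SAP*

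**What the plan says.** Section 8.6.1.1 analyses change from Day 1 in log testicular volume with a "mixed model with a fixed effect for baseline and time point and a random effect for subject" and an unstructured covariance. At each visit, "the mean change from Day 1 to that time point and the associated 95% confidence interval (CI) will be calculated", and the result is exponentiated to a geometric mean increase. The supportive completer analysis is an "Analysis of Covariance (ANCOVA) model including baseline as a covariate".

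The section does not say at which baseline value the mean change is evaluated, or whether its standard error allows for sampling variation in baseline. The Table 6 footnote describes the primary model differently, as a "Linear Mixed Model with terms for treatment", although there is only one arm.

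Section 8.3 states: "This is an estimation study, no hypothesis will be tested". Section 8.9.1 plans precision from a "difference in paired means with 10 completed subjects", which has no baseline adjustment. The objective in Section 3.1 concerns the change in adolescent boys with HH as a population.

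**The concern.** With no comparator, a baseline covariate corrects no imbalance between arms. What it does here is move part of the between-boy variation in change out of the residual. The software's default standard error for the mean change then uses only what is left, as if another sample of boys would have the same baselines.

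That suits a statement about boys at this sample's mean baseline. It does not suit a statement about the average increase in the population, which is how the objective reads. Because no hypothesis is tested, the interval is the trial's inference. If its true coverage is below 95%, the trial overstates its precision and its lower limit is too high.

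**Working it through.** **Inputs.** The model, the ANCOVA and the reported interval come from Section 8.6.1.1. From Section 8.9.1: n = 10 completers, SD of log change 0.47 (the adult trial P031), and Table 7 differences of 0.4 to 0.8 with SDs of 0.45 to 0.55. The documents do not give the correlation r between change and baseline, the baseline to Week 64 correlation ρ, or the separate SDs at the two visits. These are assumed and varied below.

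**Step 1: the plan's own figure.** For difference 0.8 and SD 0.45, Table 7 prints 2.23 (1.76, 2.81). This reproduces as exp(0.8 ± 1.645 × 0.45/√10). The multiplier 1.645 reproduces all 15 rows to within 0.005; 1.960, t₉ = 1.833 and t₉ = 2.262 do not. Table 7 has no baseline term, so it neither shows nor allows for the effect examined here.

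**Step 2: the missing variance.** Let σ be the SD of change.
- With complete data, the fitted change at the sample-mean baseline equals the raw mean change, so the estimate does not move.
- Default ANCOVA variance of that mean: σ²(1 − r²)/n.
- Its variance as an estimate of the population mean change: σ²/n.
- Difference: r²σ²/n = slope² × Var(baseline)/n. It is zero only if change is unrelated to baseline.

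**Step 3: effect on the interval** (difference 0.8, SD 0.47, n = 10). The paired interval is exp(0.8 ± 2.262 × 0.47/√10) = 1.59 to 3.11. The ANCOVA interval is exp(0.8 ± 2.306 × 0.47 × √(1 − r²)/√10):

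| abs(r) | SE factor √(1 − r²) | ANCOVA interval | Simulated coverage of population mean change |
|---|---|---|---|
| 0 | 1.00 | 1.58 to 3.14 | 95.0% |
| 0.3 | 0.95 | 1.60 to 3.09 | 94.2% |
| 0.5 | 0.87 | 1.65 to 2.99 | 92.0% |
| 0.7 | 0.71 | 1.74 to 2.84 | 86.3% |

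The coverages come from 200,000 simulated trials per row. The paired t interval covered about 95% throughout.

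**Step 4: linking r to the two visits.** If the Week 64 SD is k times the baseline SD, then r = (kρ − 1)/√(1 + k² − 2kρ). With k = 1 this is −√((1 − ρ)/2), which gives −0.71, −0.61, −0.50 and −0.32 at ρ = 0, 0.25, 0.5 and 0.8. With k = 1.5 it is −0.55 at ρ = 0, −0.19 at ρ = 0.5, and zero at ρ = 1/1.5 = 0.67.

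**Step 5: simulated coverage of the nominal 95% CI, n = 10, complete data.**

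| Analysis | ρ = 0 | ρ = 0.5 | ρ = 0.8 |
|---|---|---|---|
| Primary mixed model, equal SDs | 87.0% | 92.5% | 93.5% |
| Completer ANCOVA, equal SDs | 85.7% | 91.9% | 94.1% |
| Completer ANCOVA, Week 64 SD 1.5 times baseline SD | 90.9% | 94.7% | 94.6% |

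The mixed-model row uses three post-baseline visits, one common baseline slope, an unstructured covariance and 3,000 runs per setting. A separate simulation of that model with 6,000 runs per setting ranged from 89.6% to 93.9%, with intervals 4% to 17% narrower than the paired t interval. The low end is therefore known only to within about 3 points. More boys do not remove the effect: at n = 15 the 3,000-run simulation gave 84.9% at ρ = 0 and 93.8% at ρ = 0.8.

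**The case against.** The strongest reply is that the adjusted interval is valid conditional on the observed baselines, which is a common reading of an adjusted mean. That is correct. But the plan does not state this reading, and the objective in Section 3.1 points to the population, so the target needs to be named.

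The second reply concerns size. Equal SDs are not given anywhere. Inclusion criterion 5 (Section 5.1.2) limits baseline to below 4.0 mL per testis, with one testis allowed 4-8 mL, while Week 64 volume has no limit. A larger Week 64 SD is therefore plausible, and it shrinks the loss. At an SD ratio of 1.25 the ANCOVA covers 93.8% at ρ = 0.5 and 94.7% at ρ = 0.7. This stands: the interval may be too narrow, not must be. The lowest figures also need ρ near 0, meaning a boy's baseline volume says nothing about his Week 64 volume.

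Several stronger readings are tempting, and the documents do not support them:
- A reader might infer that the Table 7 intervals are wider than those the analysis will give. Table 7 uses 1.645. An interval 4% to 17% narrower than paired t has a multiplier of about 1.88 to 2.17 (2.262 × 0.83 to 2.262 × 0.96), so it is wider than Table 7. The ANCOVA is narrower than Table 7 only when the absolute value of r exceeds about 0.70.
- Nor does a paired t interval match Table 7. For difference 0.8 and SD 0.45 it is 1.61 to 3.07, against the printed 1.76 to 2.81. The Table 7 multiplier is a separate error, so the planned 1.7-fold lower limit is not a clean yardstick here.
- The Week 12 to Week 64 model has no baseline term, but it is not a second, conflicting primary-endpoint model. Section 8.4.1 defines the primary endpoint as Day 1 to Week 64 only.
- The P031 interval (2.03-2.62, 18 men) is narrower than an SD of 0.47 would give (1.83 to 2.93 with t₁₇). Baseline adjustment could explain that, but the documents do not say how the interval was computed, so it is not evidence of the size of r.

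**Conclusion.** The point holds in a conditional form. With baseline as a covariate in this one-arm model, the default standard error omits slope² × Var(baseline)/n, and the nominal 95% CI under-covers the population mean change whenever that slope is not zero.

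For the primary mixed model at n = 10 with equal SDs, coverage is about 87% to 90% at ρ = 0, rising to about 94% at ρ = 0.8. For the completer ANCOVA it is about 86% to 94% with equal SDs, and about 91% to 95% if the Week 64 SD is 1.5 times the baseline SD. It is nominal when change is unrelated to baseline.

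The mechanism is certain; the size is an assumption. The figures assume complete data and normal log volumes. With missing visits, the estimate itself can also move slightly. The change is worth making because the interval is the main result and the correction costs little.

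**What to change.** 1. State the target as the unconditional mean change in log volume from Day 1 to Week 64, exponentiated to a geometric mean increase.
2. Remove baseline as a covariate. Enter the Day 1 log volume as a response at time 0, with time categorical (Day 1, Weeks 12, 36 and 64), and report the Week 64 minus Day 1 contrast. With complete data this has the same estimate and standard error as the paired analysis, and it keeps the model-based handling of missing visits under MAR.
3. Name a small-sample df method, such as Kenward-Roger, and a pre-specified fallback covariance that allows variances to differ over time. Compound symmetry would force Day 1 and Week 64 to have equal variance.
4. For completers, replace the ANCOVA with the paired t interval on log change.
5. Correct the Table 6 footnote to describe this model.

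**Cost.** SAP wording and a small change to the model code. The unstructured covariance grows from 3 × 4/2 = 6 to 4 × 5/2 = 10 parameters. With 10 to 15 boys this makes non-convergence more likely, which is why the fallback in item 3 matters. The reported CI may be wider. If change turns out to be unrelated to baseline, almost nothing is lost.

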8.6.1.2 Secondary Efficacy Analysis

The change in serum inhibin B concentrations after 64 weeks will be summarized. In addition, changes from Day 1 to Week 12, and from Week 12 to Week 64 will also be summarized. A listing by subject and time point will also be provided for each treatment phase.

The growth velocity (cm/year) will be summarized as follows:

For each subject, the growth velocity over the 36 and 64 week treatment periods will be extracted using the slopes estimated from an overall mixed random intercept and random slope model of height (cm) and time (in years) and age as covariates. Overall growth velocity slope over 36 and 64 weeks will also be presented based on the same model. An unstructured covariance matrix will be used to model the correlation among repeated measurements. In the event of model convergence issues, other covariance structures (i.e. AR or compound symmetry) will be considered.

In addition, growth in cm over 12, 36 and 64 weeks will be listed for each age (14, 15, 16 and 17 years of age at randomization). Annualized growth velocity (cm/year) at 36 and 64 weeks will also be calculated and listed.

For each male subject, Tanner Staging will be recorded for both pubic hair and testicular volume. Tanner Stage of development at Baseline, week 12, week 36 and at the end of the 64 weeks of combined treatment will be summarized by shift table. A listing of Tanner Stage by time point and subject will also be provided.

Descriptions of sonographic testicular patterns will be listed at Baseline and weeks 12, 36 and 64. Any changes over time will be described.

For continuous variables, summary statistics will include the number of observations, mean, standard deviation, median, minimum and maximum. For categorical variables, frequency distributions will be provided.

Serum concentrations of hormones (LH, Total T, E2, SHBG, and AMH) will be summarized by assessment (Week 1-64). Additional summary statistics will include first and third quartile as well as geometric mean together with coefficient of variation. Values below the Lower Limit of Quantification (LLOQ) will be set to $\frac{1}{2}$ times the LLOQ for the calculation of descriptive statistics. The number and percentage of values below the LLOQ will be reported. Additionally, serum hormone concentrations will be summarized by treatment phase.

The summary of the key efficacy analyses is provided in [Table 6](#).

Table 6 Analysis Strategy for Key Efficacy Variables

Endpoint/Variable (Description, Time Point)	Primary vs. Supportive Approach [†]	Statistical Method	Analysis Population	Missing Data Approach
Primary Endpoint				
Change from Baseline to Week 64 in log-transformed testicular volume (measured as the sum of volumes of left and right testes by ultrasound);	P	Linear Mixed Model [#]	FAS	Model-based
Change from Baseline to Week 64 in log-transformed testicular volume (measured as the sum of volumes of left and right testes by ultrasound);	S	Linear Mixed Model [#]	FAS	LOCF ^{\$\$}
Change from Baseline to Week 64 in log-transformed testicular volume (measured as the sum of volumes of left and right testes by ultrasound);	S	ANCOVA	Completers	N/A

[†] P=Primary approach; S=Supportive approach.

[#] Linear Mixed Model with terms for treatment.

^{\$\$} LOCF = last-observation-carried-forward method.

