Treatment with MK-8962			Once every two weeks (first dose on Day 1/Week 0 and last dose on Day 435 /Week 62)																						
Dispense hCG ^l									X	X		X		X		X		X		X		X			
Treatment with hCG											Twice weekly (e.g., every Monday and Thursday, or every Tuesday and Friday) ^m														
Clinical Procedures/Assessments																									
Full Physical Examination	X																						X	X	
Focused Physical Examination ⁿ		X								X							X								
Vital Signs (HR, BP measured twice)	X	X							X							X							X	X	
Weight (measured twice)	X	X					X	X		X	X		X		X			X		X		X	X		
Height for Growth Velocity (measured 3 times)	X	X							X						X								X	X	
Testicular ultrasound ^o	X	(X) ^t							X						X							X	X ^p	(X) ^p	
Tanner Staging ^q	X	X							X						X							X	X		
Adverse Events Monitoring	X	X	X	X	X	X	X	X	X	X	X	X	X	X	X	X	X	X	X	X	X	X	X		

Trial Period:		MK-8962 Priming Phase									Combined Treatment Phase (MK-8962 / hCG) ^a														
		1	2	3	4	5	6	7	8	9	10		11		12		13		14		15	D/C ^b	Follow-up ^c		
Visit Number																									
Visit/Contact Title:	Screening	Treatment Allocation								TC		TC		TC		TC		TC		TC		D/C ^b			
Scheduled Week ^d :	-1	0	1	1	1	2	2	4	8	12	16	20	24	28	32	36	40	44	48	52	56	60	64 ^e		
Scheduled Study Day:	-7 to -1	1 ^f	3	5	8	11	15	29	57	85	113	141	169	197	225	253	281	309	337	365	393	421	449		+7 ^c
Scheduling Window (Days):	-42 to -1								+/- 7	+/- 3	+/- 7	+/- 3	+/- 7	+/- 3	+/- 7	+/- 3	+/- 7	+/- 3	+/- 7	+/- 3	+/- 7	+/- 7	+/- 7	+/- 7	+24
Laboratory Procedures/Assessments																									
Serum for free T4	X																								
Hematology	X	X								X							X						X	X	
Chemistry Panel	X	X							X							X							X	X	
Serum for endocrine parameters ^r : FSH, LH, hCG, inhibin-B, AMH, Calc. Free T, and SHBG	X	X								X							X						X	X ^p	(X) ^p
Serum for endocrine parameters ^r : Total T and E2	X	X								X	X		X			X			X		X		X	X ^p	(X) ^p
Pharmacokinetic (PK) sampling for MK-8962 concentration ^s		see Section 7.1.3.3.1 Flow Chart for Pharmacokinetic Assessments																							
Sampling for Anti-MK-8962 antibodies ^r		X							X	X			X			X			X			X	X	X	

AMH = anti-Müllerian hormone; E2 = estradiol; FSH = follicle stimulating hormone; hCG = human chorionic gonadotropin; HIV = human immunodeficiency virus; LH = luteinizing hormone; SHBG = sex hormone-binding globulin; TC = telephone call; T = testosterone

^a The Combined Treatment Phase starts at the end of Week 12.

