8.4.1 Efficacy/Immunogenicity/Pharmacokinetics Endpoints

Primary Efficacy Endpoint

The primary efficacy endpoint for this trial is the Change from Baseline (Day 1) to Week 64 in log-transformed testicular volume (measured as the sum of volumes of left and right testes by ultrasound).

Secondary Efficacy Endpoint

- Change from baseline in serum inhibin B concentrations at Week 64;
- Growth velocity at Week 36 and Week 64;
- Tanner Stage of pubertal development at Weeks 12, 36 and 64.
- Characterization of MK-8962 pharmacokinetics (based on serum MK-8962 concentrations) through 64 weeks of treatment.

- Characterization of testicular sonographic pattern reflecting pubertal development through 64 weeks of treatment;
- Changes from baseline in endocrine parameters (LH, calculated free testosterone, Total T, E2, SHBG, and AMH at Weeks 12, 36 and 64;

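### One straight-line random-slope model cannot give separate growth velocities for 36 and 64 weeks, so the model-based 36-week summary is biased unless growth is constant

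*Combined protocol and SAP*

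**What the plan says.** Section 8.4.1 lists the secondary endpoint as "Growth velocity at Week 36 and Week 64", that is, at two time points.

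Section 8.6.1.2 gives the method. For each subject, "the growth velocity over the 36 and 64 week treatment periods will be extracted using the slopes" of "an overall mixed random intercept and random slope model of height (cm) and time (in years) and age as covariates". For the group: "Overall growth velocity slope over 36 and 64 weeks will also be presented based on the same model". The section states no quadratic, spline, phase-specific or piecewise time term. It does not say that the model is refitted to data through Week 36, and it does not say whether age means baseline age or current age.

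Two outputs in the same section do not depend on the model: "growth in cm over 12, 36 and 64 weeks will be listed for each age", and "Annualized growth velocity (cm/year) at 36 and 64 weeks will also be calculated and listed". A later general sentence promises the usual descriptive statistics for continuous variables, without naming growth velocity.

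The column positions in the flow chart (section 6.0) are damaged in the text available. Read with the planned 12-, 36- and 64-week listing, it has height measured at screening, Day 1 and Weeks 12, 36 and 64.

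**The concern.** An endpoint defined at two times needs an estimator that can take two values. A model of height that is linear in time has the same modelled velocity over every window, so it cannot distinguish the first 36 weeks from the full 64.

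That would be harmless if growth were steady, but the design gives reason to doubt it. Section 4.2.1 describes 12 weeks of MK-8962 alone followed by 52 weeks with hCG added. Section 4.1.1 says that hCG is given to raise testosterone, and section 4.2.3.1 treats growth velocity as a marker of pubertal progress. If growth changes pace after Week 12, the pooled slope carries information from Weeks 36 to 64 into the figure reported for Week 36. At stake is the accuracy of the modelled 36-week velocity and the agreement of that summary with the plan's own listing.

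**Working it through.** The documents state no expected growth velocity, SD or precision for this endpoint, so there is no figure of the plan's to reproduce. The growth patterns and variances below are assumptions.

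**Step 1: algebra.** Write the stated model as h(i,t) = (b0 + u0i) + (b1 + u1i)·t + g·age(i) + error. The modelled velocity over any window from 0 to T is [h(T) − h(0)]/T = b1 + u1i, in which T does not appear. The difference between the 36- and 64-week values is exactly 0, per boy and overall. Baseline age shifts the intercept only. Current age would be collinear with time within a boy and would not add a period-specific slope.

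**Step 2: what the single slope estimates.** Let v1, v2, v3 be the velocities (cm/yr) in Weeks 0–12, 12–36 and 36–64, with heights at Weeks 0, 12, 36 and 64. The mean week is 28, the deviations are −28, −16, 8 and 36, and their squares sum to 2,400. The least-squares slope is then

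- single slope = (12·28·v1 + 24·44·v2 + 28·36·v3)/2,400 = 0.14·v1 + 0.44·v2 + 0.42·v3

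The targets are

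- true 36-week velocity = (12·v1 + 24·v2)/36
- true 64-week velocity = (12·v1 + 24·v2 + 28·v3)/64

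With complete data and independent residuals, the overall slope of the random intercept and slope model equals this least-squares slope. Dropout or another covariance structure changes the weights, but there is still only one slope. The single slope puts 42% of its weight on Weeks 36–64, which play no part in the 36-week target.

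**Step 3: numbers.**

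| Assumed v1/v2/v3 | True, 36 wk | True, 64 wk | Single slope | Error at 36 wk | Error at 64 wk |
|---|---|---|---|---|---|
| 6/6/6 | 6.00 | 6.00 | 6.00 | 0 | 0 |
| 5/6/7 | 5.67 | 6.25 | 6.28 | +0.61 (11%) | +0.03 |
| 4/5/7 | 4.67 | 5.69 | 5.70 | +1.03 (22%) | +0.01 |
| 4/8/10 | 6.67 | 8.13 | 8.28 | +1.61 (24%) | +0.16 |
| 4/6/9 | 5.33 | 6.94 | 6.98 | +1.65 (31%) | +0.04 |
| 4/9/6 | 7.33 | 6.75 | 7.04 | −0.29 (4%) | +0.29 |

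For 4/5/7, for example: 0.14·4 + 0.44·5 + 0.42·7 = 5.70, against (48 + 120)/36 = 4.67.

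**Step 4: check with the mixed model.** Sixty trials per scenario were simulated with 15 boys, a between-boy slope SD of 1.0 cm/yr and a residual SD of 0.3 cm (both assumed), and fitted by REML with time and age. Mean estimates:

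| Assumed growth | Single fit (serves both periods) | Refit through Week 36 | Annualized, 36 wk | Annualized, 64 wk |
|---|---|---|---|---|
| 6/6/6 | 6.03 | 6.02 | 6.01 | 6.03 |
| 4/5/7 | 5.75 | 4.76 | 4.72 | 5.74 |
| 4/6/9 | 6.91 | 5.37 | 5.27 | 6.87 |

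The single fit stays near the 64-week truth. The refit and the direct calculation recover the 36-week truth closely.

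**The case against.** Four arguments on the other side have weight.

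- **The plan has other outputs.** A reader might infer that the trial would report one number for both time points and could not show a change in growth rate. The documents do not support that. Section 8.6.1.2 also lists growth in cm over 12, 36 and 64 weeks and annualized velocity at 36 and 64 weeks. With about 15 boys enrolled, those listings show period-specific growth for everyone. The general sentence on continuous variables may even extend a mean and SD to the annualized values, though it does not say so. This argument stands and limits the point to the model-based summary.

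- **The model may be meant to be fitted twice.** The word overall could mean pooled across boys, and the reference to the same model could mean the same specification applied to each period. Reporting two periods makes more sense on that reading. It is possible, but it is nowhere stated, and the wording points more naturally to one fit. At best the text needs a sentence.

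- **The size is assumed.** The documents give no velocities and do not say that growth should accelerate after Week 12. This stands: the percentages are illustrations, and the error changes sign if growth rises and then slows.

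- **The stakes are modest.** Section 8.1 names no key secondary endpoints, section 8.3 says no hypothesis is tested, section 8.8 treats other efficacy analyses as supportive, and growth velocity is absent from Table 6. This also stands.

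Shrinkage of individual slopes adds little. Under the Step 4 SDs the slope reliability is 1/(1 + 0.09·52²/2,400) = 0.91, and shrinkage does not bias the group mean.

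**Conclusion.** The point holds for the model-based summary. Read plainly, section 8.6.1.2 produces the same modelled velocity for 36 and 64 weeks. That identity is algebraic and needs no assumption beyond a single fit that is linear in time.

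The bias in the 36-week value depends on assumed growth: about 11 to 31% too high in the accelerating scenarios, about 0.3 cm/yr too low in the rise-then-slow scenario, and zero under constant growth. The 64-week value is off by at most 0.16 cm/yr in the accelerating scenarios and 0.29 cm/yr in the rise-then-slow one. The listed annualized velocities and growth in cm remain correct, and the primary analysis is untouched. The section should be corrected, because the stated rule gives a wrong 36-week summary whenever growth is not constant and the repair is cheap.

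**What to change.** Amend section 8.6.1.2, or record the change in the supplemental SAP that section 8.0 provides for, with one of the following:

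1. **Preferred:** make the directly calculated annualized velocity, [h(T) − h(0)]/T at Weeks 36 and 64, the summarized estimate, with mean, SD and 95% CI. It matches the endpoint and is already calculated. It needs a height at both ends, so the rule for boys without a Week 64 height should be stated.
2. State that the random-slope model is fitted separately to data through Week 36 and through Week 64. This ends the identity but remains approximate when growth bends within a period. The slope through Week 36 is (192·v1 + 480·v2)/672, which gives 4.71 against 4.67 for 4/5/7 and 7.57 against 7.33 for 4/9/6.
3. Add a piecewise time term with knots at Weeks 12 and 36 and compute velocity as [h(T) − h(0)]/T. This uses all available heights. With one random slope, each boy's difference between periods would come only from the group curve, so per-boy values should still be the direct ones.

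Whichever is chosen, say whether age is baseline age.

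The cost is wording and code, since the heights are already collected. Precision at Week 36 falls slightly. Under the Step 4 assumptions (15 boys, complete data), the standard error of the mean is √[(1 + 0.09·52²/2,400)/15] = 0.27 cm/yr for the single slope and √[(1 + 2·0.09/(36/52)²)/15] = 0.30 cm/yr for the direct 36-week velocity.
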